8.4.1 Specific criteria for withdrawal

Not applicable

8.5 Replacement of individual subjects after withdrawal

If a participant withdraws from the study, he/she will not be replaced.

8.6 Follow-up of subjects withdrawn from treatment

Participants who stop participating but do not withdraw their consent will be followed according to the standard clinical protocol currently used for patients with a total hip arthroplasty for recording of any adverse events. The patient shall not be asked to perform study related activities. It will be noted in the patient file if the patient no longer wishes to participate or if the patient has withdrawn informed consent.

8.7 Premature termination of the study

Based on the Australian national register for THA, the NANOS prosthesis shows excellent low revision rates at 3 years of follow-up compared to other short stem prosthesis.

In a pilot study that was performed in our centre with the CORAIL femoral stem²¹, we analysed our own patient files for differences between the DAA and PLA. We analysed a cohort of 80 patients (83 hips) that were operated between January 2012 and December 2012 by a single surgeon in our hospital. 38 patient received a prosthesis by means of a PLA and 45 by means of a DAA. Complications and follow-up measurements did not show significant differences between the two approaches. Differences between the pre-surgery and 1 year follow-up measurements were also comparable. To our knowledge, few data is available on how surgical approach influences subsidence²². Glyn-Jones et al.²² reported no difference in subsidence between the posterolateral approach and direct lateral approach. Given the abovementioned information, we consider an interim analysis as not necessary.

9. SAFETY REPORTING

9.1 Section 10 WMO event

In accordance to section 10, subsection 1, of the WMO, the investigator will inform the subjects and the reviewing accredited METC if anything occurs, on the basis of which it appears that the disadvantages of participation may be significantly greater than was foreseen in the research proposal. The study will be suspended pending further review by the accredited METC, except in insofar as suspension would jeopardize the subjects' health. The investigator will take care that all subjects are kept informed.

9.2 AEs, SAEs and SUSARs

9.2.1 Adverse events (AEs)

Adverse events are defined as any undesirable experience occurring to a subject during the study, regardless of cause. All adverse events reported spontaneously by the subject or observed by the investigator or his staff will be recorded.

9.2.2 Serious adverse events (SAEs)

A serious adverse event is any untoward medical occurrence or effect that at any dose:

- results in death;
- is life threatening (at the time of the event);
- requires hospitalisation or prolongation of existing inpatients' hospitalisation;
- results in persistent or significant disability or incapacity;
- is a congenital anomaly or birth defect;
- Any other important medical event that may not result in death, be life threatening, or require hospitalization, may be considered a serious adverse experience when, based upon appropriate medical judgement, the event may jeopardize the subject or may require an intervention to prevent one of the outcomes listed above.

The principle investigator will report the SAEs and possible device related events through the web portal *ToetsingOnline* to the accredited METC that approved the protocol, within 15 days after the principle investigator has first knowledge of the serious adverse events. SAEs that result in death or are life threatening should be reported expedited. The expedited reporting will occur not later than 7 days after the responsible investigator has first knowledge of the adverse reaction. This is for a preliminary report with another 8 days for completion of the report.

If prolongation of hospital stay is due to logistical reasons (e.g. a patient is placed on a waiting list for a place in a rehabilitation centre); it will not be reported as an SAE.

9.2.3 Adverse device Effects

All adverse events device-related or not, must be recorded and evaluated on the basis of the relationship to the device. Specifically, all component removals (and/or revisions) whether device related (or not device related) depending on their frequency, medical significance and circumstance.

Adverse device effect: are defined as the following:

- Any device component failure (e.g. breakage)
- Device wear particle induced osteolysis inflammation etc. Wear debris may be metal and or hydroxyapatite in composition.
- Any device component experiencing dislocation subsidence subluxation or migration.
- Unintended fractures
- Nerve damage (as evidence immediate postoperative by motor/sensor deficit not present preoperatively).
- Large vessel damage (with large blood loss i.e. 1500ml).
- Hip pain is recorded as VAS score and ranked as an element in the HOOS. It is not routinely categorized as an adverse event. Extreme or persistent hip pain leading to disability may however be reported as adverse event.
- Other adverse related events that are deemed device related and serious.

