4.4 Sample size calculation

The main hypothesis of this study is that the NANOS short stem prosthesis will show less subsidence if placed by means of the DAA compared to the PLA at two years follow-up. No previous studies have been published in which differences in subsidence between DAA and PLA are compared for short stem prostheses.

The study design of the present study is an RCT. We calculated our sample size based on the study of Budde et al.¹⁵. In this study a mean subsidence of 0.46 ± 0.31 mm was measured for the NANOS stem prosthesis after 2 years of follow-up. When assuming a mean subsidence of 0.46 mm in the PLA group and 0.25 mm less subsidence in the DAA group, a sample size of 25 subjects in each group (a total of 50 subjects) is necessary to detect a difference with a power of 80% and a two-sided 5% significance level using an independent t-test.

Since the follow-up of patients is almost similar to the regular follow-up of patients that undergo total hip replacement, we do not expect a high number of patients that are lost to follow-up. Therefore, we will include 10% more patients, which resulted in 56 patients.

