8.1.2 Secondary study parameters/endpoints

Secondary study parameters are the clinical, functional and surgical outcome parameters compared between the DAA and PLA:

- Perceived pain, measured using a Visual Analogue Scale (VAS) in the week before surgery, during hospitalization at days 1 to 3, at discharge, 8 weeks, three months, six months, one year after surgery and two years after surgery.
- Hip pain and symptoms assessed using the symptoms, pain and activities of daily living (ADL) subscales of the Hip Dysfunction and Osteoarthritis Outcome Score (HOOS) in the week before surgery, at 8 weeks, three months, six months, one year after surgery and two years after surgery.
- Hip range of motion in the week before surgery, at 8 weeks, three months, six months, one year after surgery and two years after surgery.
- Quality of life assessed using the EQ-5D in the week before surgery, at 8 weeks, three months, six months, one year after surgery and two years after surgery.
- Functioning during daily living assessed using the HOOS in the week before surgery, at 8 weeks, three months, six months, one year after surgery and two years after surgery.
- Hip abductor strength and gait quality before surgery, at 8 weeks and after 12 months.
- Length of hospital stay
- Operation time, blood loss, and other parameters of the surgical procedures
- All complications related to the surgery and rehabilitation
- Health status will be classified using the ASA score.
- Patient's pre-operative status, surgical procedure as well as clinical and radiological outcome will be documented.

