8.3 Study procedures

Pre-operative assessment

After inclusion participants will be asked to fill in the questionnaires. A general questionnaire containing questions about demographic characteristics of the participants, and validated questionnaires to assess clinical and functional outcomes will be used. The Hip Dysfunction and Osteoarthritis Outcome Score (HOOS)¹⁷ will be used to assess pain, symptoms and function of the hip in relation to different activities of daily life. Also, a Visual Analogue Scale (VAS) will be used to assess perceived pain in the previous week. To assess quality of life, the participant will be asked to fill in the EQ-5D^{18,19}.

In addition to the self-reported HOOS, the quality of movement and walking will be quantified to assess functional outcome. Basic balance and gait performance will be tested using the timed “up & go” (TUG) test, instrumented with inertial sensors to measure body segment accelerations and angles, and a two times 50 meter walk at their preferred walking speed, also instrumented with inertial sensors⁸⁻¹². For the TUG test¹³, in short, participants will be asked to stand up from a chair, walk for 3 meters, walk back to the chair and sit down on the chair. The time needed to perform the TUG as instructed will be registered. In addition, the participants will wear inertial sensors (McRoberts Dynaport Hybrid, Dimensions 87 x 45 x 14 mm, Weight 74 grams)¹⁴, which will be attached to the lower back with Velcro fixation. The inertial sensors measure the accelerations and angles of the lower leg as well as stance and tilt of the pelvis. Pre-operatively, standardized calibrated radiographs of the pelvis (anterior posterior or AP and lateral views) are performed.

Measurement of subsidence:

The EBRA-FCA system measures subsidence offset and varus/valgus angulation using at least four standardized AP standing pelvic x-rays. It can detect axial subsidence of 1 mm with a specificity of 100% and sensitivity of 78%. This system has been validated for short stem hip implants and has been previously used for the NANOS stem. Progressive subsidence of >1.5 mm two years after prosthesis placement is an indicator for aseptic loosening^{5,7,20}. Subsidence will be measured by independent and blinded radiologists.

Assessments during surgery and hospital stay

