10. STATISTICAL ANALYSIS

10.1 Primary study parameter(s)

To answer our primary research question, subsidence at two years will be used. Secondary measurements include subsidence at 8 weeks and at 12 months. The EBRA-software needs at least 4 similar radiographs to correctly measure subsidence. The subsidence will be measured in mm with one decimal point behind the comma. In order to determine if there is a difference between the mean amount of subsidence (measured with the EBRA FCA) of the posterolateral and direct anterior approach group an independent t-test will be carried out and the 95% CI for the mean difference will be determined. Pearson's r will be used to calculate the effect size. The assumption of normality will be checked by visual inspection of the q-q plot and the box plot of the data within the groups. A Shapiro-Wilks test will also be performed on the data within the groups. Homogeneity of variance will be checked using the Levene's test.

The effect of time (e.g. at 1 day, 8 weeks, 12 months and 24 months postoperatively) on the amount of subsidence (measured with the EBRA FCA) will be examined with a one-way between subjects ANOVA. Eta^2 will also be calculated to determine the effect size. Tukey's HSD test will be used to identify where the specific differences occurred between the two groups. It is also used to calculate the 95% CI for each difference between the means.

The outcome parameters will be described in terms of means and standard deviations if the data are normally distributed. If the data are not normally distributed then they are described in terms of median, interquartile range and minimum and maximum values. Categorical study parameters are described as proportions.

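### Section 9.2.3 makes subsidence of any size an adverse device effect, although subsidence is the primary endpoint and is expected to be non-zero in most patients

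*Protocol*

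**What the plan says.** - **Definition.** Protocol 9.2.3 introduces its list as the definition of an adverse device effect. One item is "Any device component experiencing dislocation subsidence subluxation or migration". No size in millimetres, progression criterion, symptom or consequence is attached.
- **Other items in the same list are limited.** Large vessel damage is tied to a blood loss of 1500 ml. Nerve damage must be a new deficit seen straight after surgery. Hip pain, which is also a study outcome, normally stays out of the adverse events unless it is extreme or persistent.
- **Primary endpoint.** Section 10.1: "To answer our primary research question, subsidence at two years will be used". Readings are in millimetres to one decimal.
- **Expected values.** Section 4.4 takes from its source study "a mean subsidence of 0.46 ± 0.31 mm was measured for the NANOS stem prosthesis" and plans by "assuming a mean subsidence of 0.46 mm in the PLA group and 0.25 mm less subsidence in the DAA group".
- **Sizes the protocol treats as meaningful.** Section 8.3 gives EBRA-FCA detection at 1 mm (specificity 100%, sensitivity 78%) and adds: "Progressive subsidence of >1.5 mm two years after prosthesis placement is an indicator for aseptic loosening". Neither figure appears in 9.2.3.
- **Reporting.** Section 9.2.2: "The principle investigator will report the SAEs and possible device related events through the web portal", with a 15-day limit.
- **Complications.** Section 8.1.2 lists, among the outcomes compared between approaches, "All complications related to the surgery and rehabilitation". Section 10.2 assigns chi-square tests to categorical outcomes.

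**The concern.** One measurement has two roles. A sub-millimetre reading is the result the trial expects and analyses as its primary outcome; under 9.2.3 it is also an adverse device effect. The authors resolved the same overlap for hip pain but left it open for the primary endpoint.

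Three things are at stake. A device-event tally made up mostly of expected readings says little about breakage, fracture, dislocation or loosening. The recording and follow-up duties in 9.2.2 and 9.4 could attach to most of the trial. And if device effects are counted among the complications of 8.1.2, that comparison would partly restate the primary endpoint in dichotomised form.

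**Working it through.** **Inputs.** From 4.4: mean 0.46 mm (PLA), SD 0.31 mm, difference 0.25 mm, so the DAA mean is 0.46 − 0.25 = 0.21 mm; also "power of 80% and a two-sided 5% significance level using an independent t-test". From 10.1: resolution 0.1 mm. From 8.3: 1 mm and 1.5 mm. Two assumptions are added: a normal shape, in keeping with the planned t-test, and the same SD in both arms.

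**Step 1: reproduce the plan's figure.** Normal approximation: n per arm = 2 × (1.96 + 0.84)² × (0.31/0.25)² ≈ 24.1, rounded up to 25, or 50 in total. The exact t-test needs 25.13 per arm and has 79.8% power at 25. Allowing for 10% loss, 50/0.9 = 55.6, or 56. The stated 25, 50 and 56 reproduce, so these are the planning values in use.

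**Step 2: share of patients above a size c.** P(X > c) = 1 − Φ((c − mean)/0.31). For c = 0 this is Φ(0.46/0.31) = Φ(1.48) = 0.931 in PLA and Φ(0.21/0.31) = Φ(0.68) = 0.751 in DAA. A reading recorded as at least 0.1 mm corresponds to a value of at least 0.05 mm before rounding.

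| Size | PLA | DAA | Average | Expected of 50 |
|---|---|---|---|---|
| above 0 mm | 93.1% | 75.1% | 84.1% | about 42 |
| recorded as at least 0.1 mm | 90.7% | 69.7% | 80.2% | about 40 |
| above 1.0 mm | 4.1% | 0.5% | 2.3% | about 1 |
| above 1.5 mm | 0.04% | about 0% | about 0% | 0 |

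With 56 patients, the first row gives about 47.

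**Step 3: sensitivity to shape.** Gamma and lognormal distributions with the same means and SD give:

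- recorded as at least 0.1 mm: 98.5% to 99.96% in PLA, 60% to 79% in DAA;
- above 1.0 mm: 5.8% to 6.3% in PLA, 2.3% to 3.2% in DAA;
- above 1.5 mm: about 1% in each arm.

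The contrast between the literal rule and either size in 8.3 survives every shape tried.

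**Step 4: difference between arms that the definition alone creates.** 93.1 − 75.1 = 18.0 points for any value above 0, and 90.7 − 69.7 = 21.0 points for recorded readings. Both favour DAA, and both arise only from the hypothesised difference in the primary endpoint.

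**The case against.** **The parent definition may filter trivial readings.** Section 9.2.1 describes an adverse event as something undesirable that a subject experiences, and in 9.2.3 the word any attaches to the component, not to the amount of movement. A silent 0.2 mm reading could thus be seen as endpoint data. This is a reasonable guess at intent, but 9.2.3 is written as a definition, and the explicit hip-pain exception shows that the authors did not rely on such a filter.

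**Counting everything above zero is generous.** This stands in part. The normal model puts about 7% of PLA and 25% of DAA patients at or below zero, and most positive values lie under the 1 mm detection figure, where measurement uncertainty matters. The shares describe the rule as written; they are not a forecast of what investigators would record.

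**Stronger readings that the documents do not support:**

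- *Nearly every patient becomes a device event.* That fits PLA only. DAA is at 60% to 79% for recorded readings across the shapes tried, so most patients is the accurate wording.
- *The safety comparison repeats the efficacy endpoint.* No comparison of adverse device effects is specified, and 8.1.2 names complications, not device effects. The overlap arises only if one is counted within the other.
- *Every reading must reach the ethics committee within 15 days.* The sentence in 9.2.2 mentions possible device-related events, but it sits in the section on serious events and its clock starts from knowledge of those. The duty for non-serious device events is unclear.
- *Real events are buried while patients are being followed.* EBRA-FCA needs at least four radiographs. If these are the four postoperative time points in 8.1.1, readings come only around 24 months, so the problem lies mainly in the final tally.
- *The rule will be applied selectively.* Nothing in the protocol shows this.

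**Conclusion.** The point holds. As written, 9.2.3 makes subsidence or migration of any size an adverse device effect while the trial measures subsidence as its primary outcome and expects it to be non-zero in most patients. On the planning figures the literal rule captures about 80% to 84% of patients, against about 2% above 1 mm and almost none above 1.5 mm (about 1% under skewed shapes). This rests on the section 4.4 means and SD, a common SD and a normal shape.

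The damage is confined to device-event recording, possibly its reporting, and, only if device effects are pooled with complications, that secondary comparison. The primary endpoint, its test and the sample size are untouched. Because event definitions and reporting duties are protocol content, this is not a detail that can be left to an analysis plan.

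**What to change.** Reconcile 9.2.3 with 8.3, 9.2.2 and 10.1. Add a sentence to 9.2.3, on the model of the hip-pain item, that says when measured subsidence or migration is a device event and when it is endpoint data only. Fix it in advance and word it identically for both arms. Keep endpoint-only readings out of the complication counts of 8.1.2, and make clear in 9.2.2 which device events carry the reporting duty.

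Readings that meet the stated condition should count in both places, so that subsidence the protocol itself regards as a warning of loosening is not lost from safety. Where the limit lies is the sponsor's clinical decision. The cost is about one sentence in 9.2.3, a clarification in 9.2.2, and the need to agree on the limit; sample size, visits and the primary analysis do not change.

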9.2.4 Suspected unexpected serious adverse reactions (SUSARs)

Not applicable

9.3 Annual safety report

Not applicable

9.4 Follow-up of adverse events

All AEs will be followed until they have abated, or until a stable situation has been reached. All adverse events have to be documented on the appropriate interval and case report form. Depending on the event, follow up may require additional tests or medical procedures as indicated, and/or referral to the general physician or a medical specialist.

SAEs need to be reported till end of study within the Netherlands, as defined in the protocol

9.5 [Data Safety Monitoring Board (DSMB) / Safety Committee]

A DSMB was not deemed necessary for this study as the treatment is non-critical and does not carry substantial additional risks as stated above. Thereby no interim analysis will be performed.

10. STATISTICAL ANALYSIS

10.1 Primary study parameter(s)

To answer our primary research question, subsidence at two years will be used. Secondary measurements include subsidence at 8 weeks and at 12 months. The EBRA-software needs at least 4 similar radiographs to correctly measure subsidence. The subsidence will be measured in mm with one decimal point behind the comma. In order to determine if there is a difference between the mean amount of subsidence (measured with the EBRA FCA) of the posterolateral and direct anterior approach group an independent t-test will be carried out and the 95% CI for the mean difference will be determined. Pearson's r will be used to calculate the effect size. The assumption of normality will be checked by visual inspection of the q-q plot and the box plot of the data within the groups. A Shapiro-Wilks test will also be performed on the data within the groups. Homogeneity of variance will be checked using the Levene's test.

The effect of time (e.g. at 1 day, 8 weeks, 12 months and 24 months postoperatively) on the amount of subsidence (measured with the EBRA FCA) will be examined with a one-way between subjects ANOVA. Eta^2 will also be calculated to determine the effect size. Tukey's HSD test will be used to identify where the specific differences occurred between the two groups. It is also used to calculate the 95% CI for each difference between the means.

The outcome parameters will be described in terms of means and standard deviations if the data are normally distributed. If the data are not normally distributed then they are described in terms of median, interquartile range and minimum and maximum values. Categorical study parameters are described as proportions.

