8. METHODS

8.1 Study parameters/endpoints

8.1.1 Main study parameter/endpoint

- Radiographic analysis will be done on standard AP and lateral view X-rays postoperative, 8 weeks, 12 months and 24 months. Only the two X-rays that are taken during the extra outpatient appointment at 24 months do not include the standard treatment for THR. To measure migration and stem positioning we will use the EBRA-FCA software system. A blinded practitioner of the department of radiology will mark nineteen reference points on the stem and femur. The software automatically defines all other parameters.

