Operation parameters such as operation time and blood loss will be registered. During the first 3 days after surgery, on the second postoperative day standing AP radiographs of the pelvis will be made. The two orthopedic surgeons involved in the study have experience with placement of the NANOS stem. Each surgeon performs about 40 to 100 total hip replacements each year. Both surgeons are experienced in performing either the direct anterior approach or the posterolateral approach. The total time of hospital stay will be registered. Complications and adverse events are noted at discharge.

Follow-up assessments

A questionnaire including the HOOS, VAS, EQ-5D and complications has to be completed by the participant at the regular follow-up visits at the orthopaedic outpatient department at 8 weeks (± 14 days) and 12 months (± 31 days). In addition, the participants have to fill in the HOOS, VAS, EQ-5D at 3 and 6 months. The questionnaires will be sent to the patient's home by post or e-mail. Participants will be able to return the questionnaire without making additional costs.

At the regular visit to the orthopaedic outpatient department at 8 weeks, radiographs of the pelvis will be taken according to the standard protocol (standing AP and lateral views) extra attention will be given for correct patient positioning for later migration analysis. At the regular visit to the orthopedic outpatient department at 12 months, balance and gait performance will again be tested using the TUG test and the two times 50 meter walk, both instrumented with inertial sensors. Also at 12 months standardized standing AP radiographs of the pelvis and axial radiographs of the treated hip will be made. One additional clinical radiological follow-up visit will be scheduled 24 months after surgery. At that moment, the participant will be asked to complete the HOOS, VAS and EQ-5D and the stem positioning will be assessed using standing AP pelvis and axial hip x-rays.

Table 1: Overview of the time schedule of the assessment of the study parameters

	1**	2**	3**	4**	5	6	8**	9***
Location	OC*	IC*	IC	OC	Q*	Q	OC	OC
Assessment	Pre-op	Operation	Day 1-3	8 weeks	3 months	6 months	12 months	24 months
Window				± 14 days	± 31 days	± 31 days	± 60 days	± 60 days
Parameter								
Demographic characteristics	X							
Clinical outcome								
HOOS	X			x	x	x	x	x
VAS	X		x	x	x	x	x	x
Hospital stay			x					
EQ-5D	X			x	x	x	x	x
Complications			x	x	x	x	x	x
Functional outcome								

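### The time course of subsidence is tested as if each visit had different patients, and the Tukey step cannot compare the two approaches; the primary two-year test is unaffected

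*Protocol*

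**What the plan says.** All of this stands in Protocol section 10.1 unless another section is named.

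- **Factor.** "The effect of time (e.g. at 1 day, 8 weeks, 12 months and 24 months postoperatively" (the bracket closes there). Time is the only factor named.
- **Test.** Its effect "on the amount of subsidence (measured with the EBRA FCA) will be examined with a one-way between subjects ANOVA", with eta squared as effect size.
- **Post hoc step.** "Tukey's HSD test will be used to identify where the specific differences occurred between the two groups". On the intervals: "It is also used to calculate the 95% CI for each difference between the means".
- **Who is measured when.** Section 8.1.1: "Radiographic analysis will be done on standard AP and lateral view X-rays postoperative, 8 weeks, 12 months and 24 months". These are successive films of the same patients.
- **Reference film.** "The EBRA-software needs at least 4 similar radiographs to correctly measure subsidence". Section 8.3 places the first film after surgery thus: "on the second postoperative day standing AP radiographs of the pelvis will be made". No earlier postoperative film is scheduled.
- **Times at which subsidence is an outcome.** Two years is primary. "Secondary measurements include subsidence at 8 weeks and at 12 months". Day 1 is not among them.
- **Primary analysis.** An independent t-test of subsidence at two years, with a 95% CI.

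No section provides a repeated-measures or mixed model.

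**The concern.** A between-subjects ANOVA treats every value as coming from a different patient. Here each patient supplies a value at each visit, so patient-to-patient variation stays in the error term although it cancels from any comparison of visits. If a patient's values are positively correlated, the test is too cautious and the intervals are too wide. Continuing migration between 8 weeks and 24 months could then go unnoticed.

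Two further problems sit in the same paragraph:

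- If the first postoperative film is the reference from which migration is measured, day 1 is not an observation but a fixed zero. An overall test that includes it mainly asks whether mean subsidence differs from zero.
- Tukey's HSD is assigned a comparison that the model before it does not contain.

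At stake is the protocol's only stated analysis of the course of migration, not its primary comparison.

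**Working it through.** **1. The plan's own figure.** Section 4.4 gives SD 0.31 mm, difference 0.25 mm, two-sided 5% and 80% power.
- n per arm = 2 × (1.960 + 0.842)² × 0.31² / 0.25² = 24.1, rounded up to 25. The exact t-test gives 25.1, and power 79.8% at 25 per arm.
- 50 / 0.9 = 55.6, so 56 patients.

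Both reproduce, and neither depends on the time analysis.

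**2. Inputs for the time analysis.** From the documents: N = 50 evaluable, SD 0.31 mm, mean 0.46 mm at two years. Assumed: normal data, the same SD at each follow-up time (unless stated), and a common within-patient correlation rho, shown over a range.

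**3. Type I error for 8 weeks, 12 and 24 months (day 1 left out).** With no true change, the mean square for time has expectation σ²(1 − rho), while the between-subjects error mean square has expectation σ². The F ratio is thus shrunk by about (1 − rho), so the true error is close to P(F > Fcrit / (1 − rho)).
- On 2 and 147 degrees of freedom, P(F > f) = (1 + 2f/147)^(−73.5), which gives Fcrit = 3.06 at 5%.
- rho 0.3: f = 3.06 / 0.7 = 4.37, error about 1.4%.
- rho 0.5: f = 3.06 / 0.5 = 6.12, error about 0.3%.

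A simulation of 20,000 trials per setting agrees:

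| rho | Between-subjects type I error | Repeated-measures type I error | Power*, between-subjects | Power*, repeated measures |
|---|---|---|---|---|
| 0 | 5.0% | 5.0% | 28% | 27% |
| 0.3 | 1.4% | 4.9% | 21% | 38% |
| 0.5 | 0.26% | 5.1% | 16% | 51% |
| 0.7 | 0.01% | 5.1% | 9% | 75% |
| 0.9 | about 0 | 5.3% | 2% | nearly 100% |

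*For an assumed course of 0.36, 0.41 and 0.46 mm; only the last value is in the protocol.

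**4. Intervals between two follow-up times.** The between-subjects standard error is √(2σ²/N); the correct one is √(2σ²(1 − rho)/N). The ratio is 1/√(1 − rho):
- rho 0.3: 1.20
- rho 0.5: 1.41
- rho 0.7: 1.83
- rho 0.9: 3.16

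The Tukey 95% half-width is 0.147 mm. A paired Bonferroni interval has 0.109, 0.084 and 0.049 mm at rho 0.5, 0.7 and 0.9.

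**5. If day 1 is included as zeros.** One of four levels has no variance, so the pooled error variance falls to 0.75σ². The standard-error ratio for two later times becomes √(0.75/(1 − rho)) = 1.22, 1.58 and 2.74 at rho 0.5, 0.7 and 0.9. For day 1 against a later time it is √(2 × 0.75) = 1.22.

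Now let the mean be a constant m at all three later times. The mean square for time is about N·m²/4, so F is about N·m² / (3σ²).
- m = 0.46: 50 × 0.2116 / (3 × 0.0961) = 36.7.
- Planning means 0.46 (PLA) and 0.46 − 0.25 = 0.21 (DAA): pooled m = 0.335, pooled variance 0.0961 + 0.125² = 0.1117, so F = 50 × 0.1122 / (3 × 0.1117) = 16.7.

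The 5% critical value on 3 and 196 degrees of freedom is about 2.65. Simulation with a constant 0.46 mm (SD 0.15, 0.25 and 0.31 mm at the three times) rejected in 100% of runs.

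**6. The Tukey sentence.** A one-way ANOVA on time has visits as its groups, so Tukey's HSD yields differences between visits. Approach is not in the model. This mismatch does not depend on rho or on day 1.

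**The case against.** The strongest defence is that little depends on this paragraph. The primary question is answered by a separate t-test at two years, and every hypothesis in section 2 compares DAA with PLA; none concerns a time effect pooled over approaches. This is correct and limits the severity. It does not make the named test valid, and a wrong test named in the protocol is not simply detail left to a SAP.

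Several stronger readings are tempting, but the documents do not support them:

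- **That no DAA–PLA comparison over time is planned.** This is true of the ANOVA only. Section 10.1 calls subsidence at 8 weeks and 12 months secondary, and section 10.2 plans unpaired tests between arms at the different times for secondary continuous outcomes. Arguably those visits are covered; only a joint approach-by-time test is absent.
- **That the error could produce a false claim for one approach.** The ANOVA has no approach term, and with positive correlation its error among follow-up times is conservative.
- **That the protocol makes this ANOVA the test of loosening.** Section 8.3 gives a threshold of more than 1.5 mm at two years and does not tie it to the ANOVA.
- **That day 1 is zero as a matter of protocol text.** It is an inference, though a well-founded one: EBRA needs four films, four postoperative times are scheduled, and no earlier film shows the stem. The times are introduced as examples, and section 8.3 places the film on the second day.
- **That later contrasts become invisible.** Tukey's HSD would still report them, with low power.

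**Conclusion.** The time analysis is wrong as written and should be fixed. Two defects follow from the text alone: a between-subjects test is applied to repeated measurements of the same patients, and Tukey's HSD is asked for a comparison that its model lacks.

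The size rests on assumptions. The values of rho, the equal SDs and the 0.36/0.41/0.46 mm course are not in the documents; at rho 0 the type I error would be the nominal 5%. The 1.2 to 3.2 factor for standard errors applies only if day 1 is left out. With day-1 zeros included it is 1.2 to 2.7 for later pairs at rho 0.5 to 0.9. The near-certain significance of the overall test requires both that day 1 is the reference and that it enters the analysis.

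A reader might infer that the trial's main result is compromised. It is not: the two-year t-test and the sample size of 25 per arm stand.

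**What to change.** In section 10.1, replace the ANOVA and Tukey step with a supportive within-patient analysis of subsidence at 8 weeks, 12 and 24 months, containing approach, time and approach-by-time. A linear mixed model with within-patient covariance will do. So will a repeated-measures ANOVA with a sphericity correction.

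- Use the first postoperative film only as the reference. Keeping it as a zero level breaks sphericity: in simulation with 50 patients, an uncorrected repeated-measures ANOVA then had a type I error of about 8% at rho 0.9.
- Report within-patient contrasts between times, and the DAA–PLA difference at each time, with 95% CIs.
- State that the independent t-test at 24 months remains the sole primary analysis. Section 4.4 is powered on it, and a 24-month contrast from the new model must not become a second primary result.

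The cost is a short rewording, made before the data are analysed. It needs no extra films, visits or patients, and standard software suffices.
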